10.2 Duration of Intervention and Study

Participants will complete a total of 12-20 study visits (including baseline assessment) as shown in **Figure 1**. Intervention visits will occur over a 4-8 week period, with three follow-up visits completed over the subsequent four weeks.

10.3 Schedule of Assessments

The instruments to be used are standardized, have good psychometric properties, and are widely used. The schedule of study assessments is provided in **Table 2**.

Table 2: Schedule of Assessments

Table 2. Schedule of Assessments			TIME POINT										
Instrument Name	Purpose	Wk 0			(Wk6)					Wk 5 (9)	Wk 6 (10)	Wk 8 (12)	
		BL	Tx1	Tx2	Tx3	Tx4	Tx5	Tx6	Tx7	Tx8	1W F/U	2W	4W
Self-Reports and Consent											170		
Informed Consent X													
Demographics Form	Sample characterization	Х											
Concurrent Medications Form	Monitor medications	Х	Х	Х	Х	Х	Х	Х	Х	Х	Х	Х	Х
Treatment Services Tracking Form	Assess treatment engagement	х	Х	Х	Х	Х	Х	х	х	Х	Х	х	х
*Time Line Follow-Back (TLFB)	Primary Outcome: opioid use (amt. and frequency)	х	х	х	х	Х	Х	х	х	х	х	х	х
Beck Depression Inventory-II	Self-reported assessment of depression symptom severity	х	х	х	Х	Х	Х	х	х	х	х	х	х
Visual Analog Scale (VAS)	Measure subjective levels of opioid craving	х	Х	х	х	Х	Х	х	х	х	Х	Х	Х
General Anxiety Disorder (GAD-7)	Self report of anxiety symptom severity	х	Х	х	х	Х	Х	х	х	х	Х	Х	Х
Mystical Experiences Questionnaire	Measure of perceptual experiences		Х	Х	Х	Х	Х	х	х	Х			
Brief Pain Inventory	Measure of pain and quality of life	х		х		Х		х		х			х
University of Rhode Island Change Assessment (URICA)	Measure of motivation for change	х		х		х		х		х			х
Insomnia Severity Index (ISI)	Assess insomnia and sleep quality	х		х		Х		х		х			х
Five Facets of Mindfulness (FFMQ)	Assess aspects of mindfulness related	х		х		Х		х		х			х
PTSD Checklist (PCL-5)	Measure of PTSD symptoms	х		х		Х		х		х			х
Fagerstrom Test of Nicotine Dependence (FTND)	Measure of nicotine dependence	Х		х		Х		Х		х			х
Assessment of the Blind	Participant Perception of Randomization									Х			
Study goals	To characterize goals for treatment	х	х	х	х	Х	х	х	х	х			
	CI	inician	Assess	ments	n	1	1	1		1	n	n	
History and Physical Exam	Eligibility assessment	Х											
Vital Signs Measurement	Obtain readings of blood pressure, pulse, temperature, respirations and pulse oximetry	х	X*	X*	X*	X*	X*	X*	Х*	X*	х	х	х
Modified Observer Alertness/Sedation Scale (MOASS)	Measure of sedation		х	х	х	х	х	х	x	х	х		
Clinical Opioid Withdrawal Scale (COWS)	Clinician assessment of opioid withdrawal symptoms	Х											
*Montgomery-Asberg Depression Rating Scale (MADRS)	Primary Outcome: Clinician assessed measure of depression symptom severity	х		х		х		х		х	х	х	х
Columbia Suicide Severity Rating Scale	Assess for presence and severity of suicidal ideation	х											
Mini International Neuropsychiatric Interview	Assess for psychotic spectrum and bipolar disorder, presence and severity of OUD	х											
Pre-screening Questionnaire	To assess for basic eligibility criteria before completing a full baseline visit.	х											
Laboratory and Procedural Tests													
Pregnancy Test (female participants only)	Eligibility assessment		х	х	х	Х	Х	х	х	х			
Drug Screen	Eligibility assessment (benzos), secondary outcome measure		х	х	х	Х	Х	х	х	х	х	х	х
Serum blood tests (CBC, CMP)	Assessment of hemodynamic, hepatic, and renal function	X**											
Electrocardiogram (ECG)	Assessment of cardiac function	X**											

* Vital signs (blood pressure, pulse, and respiratory rate) will be obtained prior to treatment sessions, and at 45 and 90 minutes post-treatment. Pulse oximetry will be monitored immediately prior to treatment, and for 90 minutes after treatment. If there is an increase in systolic or diastolic blood pressure >30 mm Hg from baseline, or an increase in pulse rate >30 bpm from baseline, the measurements should be repeated after the patient has been in a resting position for 10 minutes. ** Will be performed for individuals with significant prior cardiac, renal or liver diseases.

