5.3 Exclusion Criteria

Patients will be excluded from the study if any of the following criteria apply:

- 1. They are considered an immediate suicide risk (by Columbia Suicide Severity Rating Scale of 4 or greater, a history of a suicide attempt in the past year, or by clinician judgment) or felt to be likely to require hospitalization during the course of the study.
- 2. They have a self-reported history of illicit ketamine use, or baseline urine drug testing positive for ketamine.
- 3. They are in acute opioid withdrawal (as evidenced by a score of 5 or above on the Clinician Opioid Withdrawal Scale). These subjects will be referred for clinical detoxification and pharmacotherapy induction. Subjects may be re-assessed for study eligibility after one month of treatment with a standard of care OUD pharmacotherapy.
- 4. Subjects who meet DSM-5 criteria for current bipolar disorder.
- 5. Subjects who meet DSM-5 criteria for current or history of psychotic spectrum disorders.

- 6. Women who are pregnant or nursing, and women who do not consent to use methods of highly effective birth control during the interventional phase of the study.
- 7. Subjects with current hypertension as defined by a systolic blood pressure (SBP) >140 mmHg or a diastolic blood pressure (DBP) >90 mmHg.
- 8. Subjects with a self-reported history of delirium for any cause.
- 9. A history of allergic or other adverse reaction to ketamine.
- 10. Clinically significant abnormal laboratory values, physical exam findings or self-reported medical conditions for which a transient increase in blood pressure could be significantly detrimental (e.g. glaucoma, brain aneurysms, cardiovascular disease, or end-stage renal disease).
- 11. Electrocardiogram (ECG) findings (obtained within thirty days prior to randomization) of tachycardia, prior myocardial infarction, myocardial ischemia, or aberrant conduction).

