10.4 Baseline Assessment Procedures

After completing study informed consent, participants will undergo a comprehensive evaluation to assess for inclusion and exclusion criteria. This will include self-reports, clinician assessments, and laboratory tests as shown in Table 1. This will include assessment of depression severity, and participants at highest risk for suicidality will be excluded. The comprehensive exam will also include a history and physical exam by the study PI (pulse oximetry measurements will be a component of the respiratory evaluation), baseline medication evaluation for potential harmful interactions, laboratory panels (including assessment of renal and hepatic function), and electrocardiogram to ensure safe study participation. Baseline assessments may be conducted by telehealth with vital signs to be provided by participant's home or pharmacy measurement.

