11.0 SPECIMEN COLLECTION AND BANKING

Data will be in the form of self-reported questionnaires, medical record review (including labs and pertinent medical history for the purpose of eligibility clarification), urine and breath samples, physical exam and electrocardiogram and structured clinical interviews conducted by the PI. This data will be obtained specifically for research purposes. No biologic specimens will be stored for future use. Serum based laboratory tests (complete blood counts, complete metabolic panels) and electrocardiograms will be conducted using MUSC's clinical laboratories with test results entered into the participant's electronic medical record.

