Pre-Intervention Assessment: A comprehensive exam will be conducted as part of the baseline assessment to minimize risks from study participation. This will include assessment of depression severity, and participants at highest risk for suicidality will be excluded. Participants will also be required to be in buprenorphine treatment for at least a one month period prior to study participation. The comprehensive exam will also include a history and physical exam by the study PI (pulse oximetry measurements will be a component of the respiratory evaluation), baseline medication evaluation for potential harmful interactions, and electrocardiogram to ensure safe study participation.

Peri-Intervention Monitoring: Subjects will be continuously medically and psychiatrically monitored throughout the course of the intervention and for a minimum of two hours after (or until any distress or dissociative symptoms reach clinically insignificant levels, and blood pressure returns to within 20% of their baseline values). Subjects will be instructed not to eat for at least 2 hours before taking the intervention sessions and not drink liquids at least 30 minutes after the intervention sessions to reduce the risk of nausea and vomiting. Emergency services will be immediately and continuously available on MUSC premises in the event of any medical complications. Subjects will not be allowed to drive themselves after the interventional visits, and alternative transportation will be arranged if needed.

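### The Table 2 ** footnote limits the only scheduled ECG and CBC/CMP to people with known organ disease, against sections 10.4, 11 and 13 (ECG only) and exclusion criterion 11

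*Combined protocol and SAP*

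**What the plan says.** Table 2 in section 10.3 has one row for serum blood tests (CBC, CMP) and one for the ECG. Each is marked at baseline only, with a double asterisk. The footnote to that mark reads: "Will be performed for individuals with significant prior cardiac, renal or liver diseases".

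Four other places bear on the same tests:

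- **Section 10.4** says consented participants have a full evaluation against the eligibility criteria. It lists "laboratory panels (including assessment of renal and hepatic function), and electrocardiogram to ensure safe study participation" with no limit to people with prior disease. It also says: "This will include self-reports, clinician assessments, and laboratory tests as shown in Table 1". The assessment schedule, however, is labelled Table 2. The section ends by allowing baseline assessments by telehealth, with vital signs measured at home or at a pharmacy.
- **Section 11** says the blood counts, metabolic panels and ECGs are run in the institution's clinical laboratories, again without a limit. It also allows "medical record review (including labs and pertinent medical history for the purpose of eligibility clarification".
- **Section 13**, under pre-intervention assessment, lists "baseline medication evaluation for potential harmful interactions, and electrocardiogram to ensure safe study participation". It does not list laboratory panels.
- **Section 5.3** excludes, under criterion 11, on "Electrocardiogram (ECG) findings (obtained within thirty days prior to randomization) of tachycardia, prior myocardial infarction, myocardial ischemia, or aberrant conduction". Criterion 10 excludes on "Clinically significant abnormal laboratory values, physical exam findings or self-reported medical conditions for which a transient increase in blood pressure could be significantly detrimental", with the examples "glaucoma, brain aneurysms, cardiovascular disease, or end-stage renal disease".

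**The concern.** The footnote and the text cannot both be followed for a patient with no known cardiac, renal or liver disease. Criterion 11 stands apart from the self-reported conditions in criterion 10, so its added value lies in what the patient does not know or report. The footnote removes the test from that group.

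What is at stake is safety and the consistent use of the eligibility criteria. The plan names a transient rise in blood pressure as the most clinically significant physical adverse event of ketamine (section 15.2). Staff who work from the schedule could randomize and dose a patient whose ECG, had it been done, would have excluded them.

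**Working it through.** **Step 1. Set the texts side by side.**

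| Place | ECG | CBC/CMP | Limited to prior disease? |
|---|---|---|---|
| Table 2, ** footnote | baseline only | baseline only | Yes |
| Section 10.4 | listed | listed | No |
| Section 11 | listed | listed | No (its subject is where the tests are run) |
| Section 13 | listed | not listed | No |
| Criterion 11 | required, within thirty days | – | No |
| Criterion 10 | – | uses laboratory values | No |

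The footnote does not say that others go untested. But a condition placed on the sole scheduled time point has no other sensible reading. The conflict with section 13 concerns the ECG alone; the laboratory conflict is with 10.4 and 11.

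**Step 2. Apply the criteria if 10.4 is followed.** Everyone has an ECG and laboratory results. Criteria 10 and 11 work as written.

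**Step 3. Apply them if the footnote is followed**, for a patient with no known disease.

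- Criterion 11: a fast rate would show on the baseline pulse. An unrecognized old infarction, ischemia or a conduction abnormality would not show without an ECG. The criterion does not require that the study perform the ECG, so one already on file from the thirty-day window would serve. Without one, these three findings cannot be judged.
- Criterion 10: the examination and self-report limbs still work. The laboratory limb depends on existing records.

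**Step 4. Size of the exposure.** From section 12.3, 15 patients per arm; from sections 10.1 and 12.1, 8 treatments each and an optional 8 ketamine sessions for placebo patients.

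- Randomized phase: 15 patients, at most 15 × 8 = 120 ketamine injections.
- If every placebo patient takes the option: 30 patients, at most 30 × 8 = 240 injections.
- At the 29.8% that section 15.2 takes from earlier studies, a transient pressure rise is expected in 0.298 × 15 = 4.5 to 0.298 × 30 = 8.9 patients.

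This counts who is exposed to the drug and its pressure effect. It does not measure the risk from a missed ECG finding.

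**Step 5. Effect on the primary outcomes.** The first (consent among those eligible on initial screening) is settled before any ECG, so it does not change. The second is completion among those who consent. Section 12.2 expects 60%, which for 30 consented is 18 completers. The plan's margin reproduces closely: 1.96 × √(0.6 × 0.4 / 30) = 17.5 points, against 17% stated in section 12.3.

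If k patients are excluded after consent and 60% of the rest complete, the rate is 0.6 × (30 − k) / 30:

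| k | Completers | Completion rate |
|---|---|---|
| 0 | 18.0 | 60% |
| 1 | 17.4 | 58% |
| 2 | 16.8 | 56% |
| 3 | 16.2 | 54% |

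Each extra exclusion costs about 2 points, which is small against the margin.

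**The case against.** The strongest reply is that the footnote is an isolated outlier. Sections 10.4, 11 and 13 and criterion 11 all point the other way. The study runs on one campus, and the principal investigator does the history and examination and observes each dose. In practice every participant may well get an ECG. This stands: the harm is conditional on staff following the schedule. It does not remove the conflict, because the schedule is a natural working reference for what to do at a visit and no text ranks it below the narrative.

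A second reply is that the footnote is a deliberate, risk-based choice, and that 10.4 imports it by pointing to a table. The pointer names Table 1. Even if Table 2 was meant, the later sentence that names the panels and the ECG carries no condition, and section 13 cites no table. A deliberate relaxation would also have required a change to criterion 11.

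A third reply is that other safeguards are enough: history and examination, the blood pressure limits of criterion 7, criterion 10, at least two hours of observation with emergency services at hand, withdrawal after a sustained rise above 30 mm Hg or 30 bpm, and treatment of marked hypertension. They lower the risk and deserve credit. None shows a silent ECG finding before dosing.

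A reader might infer that the footnote tests only people who are excluded anyway. The documents support this only in part. Criterion 10 names cardiovascular disease and end-stage renal disease, but not liver disease or milder renal disease, and testing known disease to judge whether it disqualifies is coherent.

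**Conclusion.** The conflict is real and should be corrected. If the footnote is followed, criterion 11 (tachycardia apart) cannot be applied to a patient without known disease who has no ECG on file from the thirty-day window, and the laboratory limb of criterion 10 rests on existing records. If 10.4 is followed, neither problem arises.

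A reader might go further and infer that patients without known disease will be dosed without an ECG, or try to attach a probability to a missed finding. The documents support neither. Most of the text calls for an ECG for all, and no prevalence of silent ECG abnormality is given from which a probability could be computed. Nor does the point touch the validity of the results: the sample size, power and efficacy analyses do not change, and the effect on the completion outcome is about 2 points per extra exclusion, assuming 30 consented and 60% completion among the rest.

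A separate and minor matter is criterion 2, which excludes on a baseline urine test positive for ketamine. The only panel described (section 4.3) covers eight drug classes without ketamine. Table 2 marks no drug screen at baseline; the first is at Tx1, before dosing under section 10.6, and the eligibility purpose given is benzodiazepines. Section 4.3 does not say that this panel is the sole eligibility assay, and self-reported illicit use still excludes.

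**What to change.** Delete the ** condition in Table 2, so that every participant has an ECG (within thirty days) and a CBC/CMP before randomization, as 10.4 states. Add to 10.4 that, when the baseline visit is by telehealth, these two items need an in-person step or a recent result on file. Correct the table reference in 10.4 to Table 2. The opposite edit, bringing 10.4, 11 and 13 into line with the footnote, would leave criterion 11 unusable for patients without known disease unless that criterion were also rewritten to apply only when an ECG is indicated. That is a clinical judgement which the current text does not make.

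Measured against 10.4, the main change is one of wording. Measured against the footnote, it adds one ECG and one blood set for each patient without prior disease: 30 × (1 − q), or 30, 27 or 24 sets if the share q with prior disease is assumed to be 0%, 10% or 20% (the documents give no figure), plus any who consent but are not randomized. Telehealth baselines gain an in-person step unless recent results are on file. A few more post-consent screen failures are possible.

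For criterion 2, either add a ketamine assay to a urine screen before randomization and mark it in Table 2, at a minor test cost, or delete the urine limb at no cost.

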10.4 Baseline Assessment Procedures

After completing study informed consent, participants will undergo a comprehensive evaluation to assess for inclusion and exclusion criteria. This will include self-reports, clinician assessments, and laboratory tests as shown in Table 1. This will include assessment of depression severity, and participants at highest risk for suicidality will be excluded. The comprehensive exam will also include a history and physical exam by the study PI (pulse oximetry measurements will be a component of the respiratory evaluation), baseline medication evaluation for potential harmful interactions, laboratory panels (including assessment of renal and hepatic function), and electrocardiogram to ensure safe study participation. Baseline assessments may be conducted by telehealth with vital signs to be provided by participant's home or pharmacy measurement.

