7.0 SETTING

All procedures will be conducted in private research study rooms on MUSC campus.

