10. STUDY DESIGN/METHODS

10.1 Study Overview

This is a double blind, placebo-controlled trial to assess the efficacy and safety of twice weekly intramuscular injections of ketamine in decreasing symptoms of OUD and MDD. Subjects will participate in a baseline visit to complete informed consent as well as complete assessments to evaluate study

eligibility and collect baseline data. Eligible participants will return within one week for the initial ketamine intervention procedure. Immediately prior to the interventional procedure, participants will be guided through a mindfulness-based exercise to facilitate relaxation and reduce anxiety during the intervention. Participants will be subsequently monitored for 120 minutes, during which time they will complete measures assessing their perception of the interventional experience. Participants initially assigned to the placebo group may choose to optionally complete 8 ketamine medication sessions beginning in Study WK #5.

	Groups A & B							
Visit #1: Baselir	ne Assessments		Study WK #0					
Visit #2: 1st Tx	Visit #3: 2nd Tx		Study WK #1					
Visit #4: 1st Tx	Visit #5: 2nd Tx		Study WK #2					
Visit #6: 1st Tx	Visit #7: 2nd Tx		Study WK #3					
Visit #8: 1st Tx	Visit #9: 2nd Tx		Study WK #4					
Visit #10: 1 WK follow-up	Visit #10: 1st KET Tx	Visit #11: 2nd KET Tx	Study WK #5					
Group A (Ketamine)		Placebo): Optional Visits						
Visit #11: 2 WK follow-up	Visit #12: 3rd KET Tx	Visit #13: 4th KET Tx	Study WK #6					
	Visit #14: 5th KET Tx	Visit #15: 6th KET Tx	Study WK #7					
Visit #12: 4 WK follow-up	Visit #16: 7th KET Tx	Visit #17: 8th KET Tx	Study WK #8					
	Visit #18: 1 WK follow-up		Study WK #9					
	Visit #19: 2 WK follow-up	2	Study WK #10					
		2 2	8					
			l					

Visit #20: 4 WK follow-up

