10.6 Intervention Visit Procedures

Prior to administration of the study compounds, participants will complete self-report questionnaires, urine testing, and clinical assessments. They will subsequently complete a 10-minute mindfulness-based psychological relaxation exercise and fill out a questionnaire regarding their study goals. Participant will be asked to disinfect their shoulder using an alcohol wipe, and the study physician will then administer the medication by intramuscular administration into the participant's deltoid muscle. Vital signs will be monitored prior to treatment, and at 45 and 90 minutes post-treatment, and blood oxygen levels will be continuously monitored using pulse oximetry. If during the post-administration observation period, ketamine administration causes an increase in systolic or diastolic blood pressure >30 mm Hg from baseline, or an increase in pulse rate >30 bpm from baseline, the measurements should be repeated after the patient has been in a resting position for 10 minutes. If the criterion is still met, then that patient will not receive further administration of ketamine and will be withdrawn from the study. After completion of the injection, participants will be monitored for 120 minutes, during which time they will undergo debriefing and complete assessments of their perceptual experience of the intervention. We will evaluate the effects of a twice weekly interventions for 4 weeks, and monitor outcomes over an additional 4-week follow-up period to inform pharmacotherapy frequency in future clinical trials. Follow-up visits may be conducted by telehealth.

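### Section 10.4 lets a home or pharmacy reading settle the 140/90 blood-pressure exclusion, and nothing requires the on-site pre-dose reading to meet that limit

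*Combined protocol and SAP*

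**What the plan says.** Section 5.3, criterion 7, excludes "Subjects with current hypertension as defined by a systolic blood pressure (SBP) >140 mmHg or a diastolic blood pressure (DBP) >90 mmHg". It names no device, setting, repeat or time point. Criterion 11, by contrast, carries a date: "Electrocardiogram (ECG) findings (obtained within thirty days prior to randomization".

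Section 10.4 makes the baseline evaluation the step at which inclusion and exclusion are assessed. It then adds: "Baseline assessments may be conducted by telehealth with vital signs to be provided by participant's home or pharmacy measurement". Section 10.1 moves on from there: "Eligible participants will return within one week for the initial ketamine intervention procedure".

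An on-site reading before dosing is scheduled. The Table 2 footnote in section 10.3 says "Vital signs (blood pressure, pulse, and respiratory rate) will be obtained prior to treatment sessions", and section 10.6 says "Vital signs will be monitored prior to treatment, and at 45 and 90 minutes post-treatment". Section 7.0 places the work on campus: "All procedures will be conducted in private research study rooms on MUSC campus". Neither the footnote nor section 10.6 gives a pre-dose value at which the injection is withheld.

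**The concern.** Section 15.2 ranks a temporary rise in blood pressure as the physical risk of ketamine with the greatest clinical importance, and exclusion 7 is the protocol's numeric entry limit against it. For a participant screened by telehealth, that limit may have been applied only to a value obtained at home or in a pharmacy. The first value measured by staff then comes just before the injection, and the plan does not say it must meet the same limit. A participant who reads 150/95 on campus could be dosed without departing from any explicit instruction.

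What is at stake is whether all participants enter treatment under the same safety limit. Estimation and testing are not touched.

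**Working it through.** **1. The rules side by side.** The plan has no figure of its own to reproduce here. Each numeric blood-pressure rule was checked for whether it would stop a first injection.

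| Rule | Where | Would it hold the first dose? |
|---|---|---|
| >140 or >90 | 5.3, criterion 7 | Only if the investigator applies it to the pre-dose value; no section says so |
| Rise >30 mmHg from baseline, then withdrawal if confirmed | 10.6 | No; limited to the period after dosing |
| Rise >30 mmHg from baseline, then repeat after rest | Table 2 footnote | May cover pre-dose readings, but asks only for a repeat |
| Return to within 20% of baseline | 13.0 | No; acts after dosing |
| Treat above 180/105 | 15.2 | No; governs treatment of a rise |

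The two relative rules depend on a baseline that is not defined and could be the home reading. Suppose, as assumed values, a home reading of 135/85 and an on-site reading of 150/95. The difference is 15/10 mmHg, so the >30 mmHg rule is not triggered although both on-site values exceed the entry limit.

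**2. Illustration of the risk.** Inputs from section 15.2: systolic rise 19.6 +/- 12.8, diastolic rise 13.4 +/- 9.8, rise seen in 29.8% of participants, treatment thresholds 180 and 105. Assumptions: +/- is a standard deviation, the rise is normal and independent of the starting value, and one ketamine session is considered. The source data are intravenous, whereas this trial injects intramuscularly.

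For starting value s and threshold T, the outer bound (everyone has the rise) is 1 − Φ((T − s − mean)/SD). Multiplying by 0.298 confines the rise to those affected, which is closer to the wording of section 15.2.

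| Start | Calculation | Outer bound | × 0.298 |
|---|---|---|---|
| SBP 140 (at limit) | 1 − Φ(20.4/12.8) | 5.5% | 1.7% |
| SBP 145 | 1 − Φ(15.4/12.8) | 11.4% | 3.4% |
| SBP 150 | 1 − Φ(10.4/12.8) | 20.8% | 6.2% |
| DBP 90 (at limit) | 1 − Φ(1.6/9.8) | 43.5% | 13.0% |
| DBP 95 | 1 − Φ(−3.4/9.8) | 63.6% | 18.9% |
| DBP 100 | 1 − Φ(−8.4/9.8) | 80.4% | 24.0% |

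The relevant quantity is the difference from an eligible patient at the limit. At 5 mmHg above it:

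- Systolic: 3.4 − 1.7 = about 2 points (outer bound 11.4 − 5.5 = about 6).
- Diastolic: 18.9 − 13.0 = about 6 points (outer bound 63.6 − 43.5 = about 20).

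**3. Cost to the feasibility outcome.** Primary outcome 2 (section 4.1) is the share of consented participants who complete. Take 30 consented and the 60% completion anticipated in section 12.2, which gives 18/30. One failure at Visit 2 gives 29 × 0.6/30 = 58.0%, or 17/30 = 56.7% if that person would certainly have completed. The loss is 2.0 to 3.3 points each. Three failures (an assumed number) give 27 × 0.6/30 = 54.0%, or 15/30 = 50.0%. The margin at n = 30 is 1.96 × √(0.6 × 0.4/30) = 17.5 points, stated as 17% in section 12.3, so a loss of 6 to 10 points lies inside it.

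**The case against.** The strongest reply is that criterion 7 already does the work. It excludes *current* hypertension and carries no date, so it can be read as binding on any reading up to the first dose; an ECG needs a window because it may be weeks old. Table 2 labels the pregnancy test and drug screen at treatment visits as eligibility checks, so eligibility does not plainly close at baseline. Telehealth is optional, consent is taken at the research offices (section 9.2), the PI observes every dose (section 3.3), monitoring lasts at least two hours (section 13.0), and the PI may withdraw anyone at any time (section 14.0).

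All of this stands and lowers the weight. It shows that a hold is permitted, and a careful investigator would probably impose one. It does not show that a hold is required. The same Table 2 describes the vital-signs row only as obtaining readings, with no eligibility purpose.

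Three stronger readings are tempting, and the documents do not support them.

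- A reader might infer that blood pressure goes unchecked by staff before dosing. It is scheduled before every session; what is missing is a limit attached to it.
- A reader might infer that remotely screened participants are never physically examined, since the examination is marked only at baseline and exclusion 10 relies on "Clinically significant abnormal laboratory values, physical exam findings or self-reported medical conditions". Section 10.4 still requires the PI's examination and names a remote substitute only for vital signs. At most, the plan could clarify when the examination takes place.
- A reader might take the 64% and 80% diastolic figures as the effect of the gap. They are outer bounds, and a patient exactly at the limit already has about 44% on the same basis. Passing 180/105 also triggers treatment and monitoring; it is not in itself an injury.

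**Conclusion.** The point holds as a cheap safety improvement of minor weight. The plan allows exclusion 7 to be judged on a home or pharmacy value, and no section requires the scheduled on-site pre-dose value to meet 140/90. Harm would need both a home reading that missed the problem and a physician who dosed despite a high recorded value.

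This conclusion rests on the text alone. The risk increments (about 2 points systolic and 6 diastolic at 5 mmHg above the limit) depend on the normal model, the intravenous source data and assumed starting values. How many participants would be affected is unknown. It would go too far to say that the plan exposes hypertensive patients to ketamine as a matter of course.

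**What to change.** - State in section 10.4 that vital signs obtained by telehealth are provisional.
- In section 10.6, require the on-site pre-dose blood pressure to be at or below 140 systolic and 90 diastolic before the first study injection. Require the same before a placebo participant's first optional ketamine injection in Week 5, because a check at the first study injection would by then be about four weeks old.
- If the value is high, repeat it after 10 minutes' rest, a step the protocol already uses. If it is still high, do not dose, and state whether the visit may be rescheduled once before exclusion.
- Where the timing allows, confirm the value before the pharmacist allocates treatment.
- Optionally, clarify when the PI's physical examination takes place after a telehealth baseline.

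**Cost.** Protocol wording, and about 10 minutes when a repeat is needed; the reading itself is already scheduled. A few consented participants may fail at Visit 2 and count as non-completers, at 2.0 to 3.3 points of primary outcome 2 each. Those who fail at the baseline visit already count this way, because consent comes first. Anyone already randomized but not dosed stays in the intention-to-treat set, which is the reason to check before allocation.
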